5 STUDY POPULATION

In this study, we aim to evaluate the PedsBP CDS in up to 45 primary care clinics with an estimated total of 216 primary care providers and 360 rooming staff. The majority of sites are staffed by family practice physicians (n=31). Pediatricians (n=2), both family practice and pediatricians (n=4) or advanced practice providers alone (n=8) cover the remaining sites.

Based on prep data, we estimate that over the 18-month study period there will be 44,061 unique patients 6-17 years with BP, height and weight recorded, with an average of 2.02 visits per patient over the study period. Similar to demographics of the region, the population is 90% white, non-Hispanic. Fifteen percent of youth receiving care at these sites are obese, with BMI $\geq 95^{\text{th}}$ percentile. Elevated BP is common (10-20% of patients with at least 1 BP meeting

criteria for elevated BP), yet diagnoses for hypertension were only found in 120 (<0.3%).

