8.2 SAMPLE SIZE DETERMINATION

Aim 1. Preliminary data from EH indicate there were 44,061 unique patients age 6-17 with visits to the 45 largest EH primary care clinics in an 18-month period. This data also indicates that 16% (n=7,258) of patients age 6-17 years had an elevated BP at initial measurement and BP re-measurement occurred at 30% (n=2210) of encounters with an elevated BP. The initial PedsBP trial had a clinic-level ICC for BP re-measurement of 0.03 and BP re-measurement of 28% in UC and 47% in the PedsBP arm.²³ With an expected 7,258 patients (161 per clinic), this study has 99% power for the H1 comparison of low- plus high-intensity clinics (30 clinics) with 15 UC clinics (alpha=.05, two-sided test, ICC=0.03) to detect a raw BP re-measurement difference of 15% between the usual care arm (30%) vs. low- plus high-intensity arms (45%). The minimum detectable difference with 80% power is 8% (30% UC vs. 38% low- plus high-intensity arms). With an expected 4,840 patients (161 per clinic), this study has 80% power for the H2 comparison of low-intensity (15 clinics, 2420 patients) vs. high-intensity clinics (15 clinics, 2420 patients), with alpha=.05, two-sided tests, ICC=0.03, to

detect a minimum detectable difference in BP re-measurement of 10% between the low-intensity arm (40%) vs. the high-intensity arm (50%).

Aim 2. Based on the prior Peds & TeenBP trial²⁴, along with observational studies of pediatric HTN¹⁰⁻¹² we anticipate 2% of patients age 6-12 and 3% of patients age 13-17 will newly meet HTN criteria at a visit over 18 months, yielding a sample size of 1060 patients (24/clinic). The PedsBP study found that 21% of patients newly meeting HTN criteria were recognized over 6 months in UC and 55% in the PedsBP arm²⁴, and the clinic-level ICC for HTN recognition was 0.035. With 1060 patients (24/clinic) and 45 clinics, this study has 99% power (alpha=.05, two-sided test, ICC=0.035) for H3 to detect a difference in HTN recognition of 17% between UC (20%) and the low- plus high- intensity arms (37%), and a minimum detectable difference of 11% (20% UC vs. 31% low- plus high-intensity arms) at 80% power. For H4 the minimum detectable difference at 80% power for HTN recognition among 706 patients (24/clinic) is 14% between low-intensity (30%) and high-intensity (44%) arms. Power computations account for the design effect due to clinic randomization and unequal counts of clinics in some comparisons and were conducted with PASS 2019.

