11 APPENDIX 1 – ASSESSMENT OF RISK FACTORS

Assessment of Cardiometabolic Disease Risk Factors and Health-Related Social Needs in Pediatric Patients with and without IDD

Background and Rationale:

Cardiometabolic risk in childhood and adolescence is associated with future disease and cardiovascular mortality^{1,2,3}. Although precise definitions and cut-offs may vary, cardiometabolic and cardiovascular disease (CVD) risk in childhood and adolescence can be measured across five domains (blood pressure (BP), lipids, glucose/Hgb A1c, smoking, body mass index (BMI)). Of these, BP and BMI are routinely assessed at all pediatric primary care visits, smoking status may be assessed during adolescent well visits, and lipids and glucose/Hgb A1c may only be assessed in patients with obesity or other risk factors^{4,5,6}.

People with Intellectual and Developmental Disabilities (IDD) have higher rates of cardiometabolic risk factors and cardiovascular disease compared to similar patients without IDD^{7,8}. There is evidence that this risk begins to accumulate in childhood, but there is a lack of data describing the prevalence of CVD risk factors in pediatric patient populations with IDD. In order to learn how to better serve pediatric patients with IDD and their families and prolong length and quality of life for individuals with IDD, better data on risk factors and areas for potential risk modification are needed.

Essentia Health started routinely collecting data on patients' health-related social needs (HRSN) in 2020 in all primary care visits. This includes personal and medical transportation, food scarcity and food insecurity, and financial strain aimed to identify those report any adverse social conditions that can contribute to poor health^{9,10,11}. Prior studies have noted an association between CVD risk and HRSN¹².

The PedsBP clinical decision support (CDS) tool has potential to improve BP measurement, remeasurement and control, as well as raise awareness of CVD risk factors and work up for secondary causes¹³. Assessment of HRSN routinely occurs in primary care clinics and association of HRSN and CVD risk factors is important to describe.

This cross-sectional analysis utilizes the baseline data from patients' PedsBP CDS index visit obtained from web service call data that is gathered at the index visit, as well as historical data prior to the index visit that will be gathered from the EHR.

Aims:

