1. In youth 6-17 years of age, describe the assessment of CVD risk factor and HRSN data in the EHR by:
 - a. rural vs urban dwelling
 - b. male vs female sex
 - c. IDD vs non-IDD
2. In youth 6-17 years of age with CVD risk factor and HRSN assessment in the EHR, describe the prevalence of CVD risk factors and HRSN:
 - a. rural vs urban dwelling
 - b. male vs female sex
3. Describe the association of CVD risk factors and HRSN.
4. Determine the prevalence of having one or more- cardiometabolic risk factors among a cohort of pediatric patients 6-17 years receiving care in a large, primarily rural health system with a diagnosis of IDD (as defined by

ICD-10 diagnostic codes for IDD). Compare this prevalence with that of patients of similar age in the health system without IDD diagnosis.

Hypotheses:

1. Comparing study-eligible pediatric patients on the assessment of CVD risk factor and HRSN data:
 - a. Assessment of CVD risk factors and HSRN will be more complete in urban-dwelling than rural-dwelling pediatric patients.
 - b. Assessment of CVD risk factors and HSRN will be more complete in female than male pediatric patients.
 - c. Assessment of CVD risk factors and HSRN will be more complete in patients with IDD than patients without IDD.
2. Comparing study-eligible pediatric patients on the prevalence of CVD risk factors and HRSN:
 - a. Rural pediatric patients will have a higher prevalence of CVD risk factors and HRSN than urban pediatric patients.
 - b. Male pediatric patients will have a higher prevalence of CVD risk factors and HRSN than female pediatric patients.
3. Patients with a higher count of HRSN will be more likely to have any CV risk factors.
4. Among those with at least two documented cardiometabolic risk measures, those with IDD will have increased CVD risk, compared with those with no IDD diagnosis.

Population: All PedsBP study-eligible patients aged 6-17 years on the date of a potential index visit (first visit) at a randomized Essentia Health clinic between August 1, 2022, to July 31, 2023.

Exclusion Criteria: Opted out of use of their data for research prior to performing analyses.

Informed Consent: See Section 9.1.1 above.

Main Measures: A complete list of variables that will be collected can be found in the data dictionary (separate document located in the study file).

Variable	Description	Data Source
Patient Description	Age, sex, race, ethnicity, vitals, labs, medications, diagnoses, encounters	CDS, EHR Clarity

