The prevalence of CVD risk factors will be computed as: a) the prevalence of any risk factor among the five of interest, and b) the prevalence of each individual risk factor. HRSN prevalence will be computed as the presence of any HRSN present. These summaries will be computed for all patients having CVD risk factor assessment (and HRSN assessment) from Aim 1 and stratified individually and multiply by patient dwelling (rural, urban), patient sex, patient age group. Differences in prevalence as defined above will be assessed with logistic regression analysis predicting prevalence from patient factors used as stratification variables. In addition, multiple linear regression will be used to assess the association of count of CVD risk factors with patient factors. Models will include the stratification factors listed above.

Aim 3. Describe the association of CVD risk factors and HRSN.

The association of any CVD risk factor (0/1) with presence of HRSN (0/1) overall and stratified individually and multiply by patient dwelling, patient sex, patient age group will be assessed in contingency table analysis and tested via Pearson and Cochran-Mantel-Haenszel chi-square tests. The association of each CVD risk factor with presence of HRSN (0/1) will be addressed with the same approach.

Multiple linear regression will be used to assess the association of count of CVD risk factors with presence of HRSN (0/1). Models will include the stratification factors listed above. One set of models will exclude any interactions and a second set will include interactions in order to formally test for differences in the association of count of CVD risk factor and HRSN by subgroups (e.g., patient age group).

Aim 4. Describe the prevalence of having one or more CVD risk factors in patients with a diagnosis of IDD vs. no diagnosis.

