The prevalence of CVD risk factors will be computed as: a) the prevalence of any risk factor among the five of interest, and b) the prevalence of each individual risk factor. HRSN prevalence will be computed as the presence of any HRSN present. These summaries will be computed for all patients having CVD risk factor assessment (and HRSN assessment) from Aim 1, and multiply stratified by IDD vs. non-IDD and patient age group. Differences in prevalence as defined above will be assessed with logistic regression analysis predicting prevalence from IDD vs. non-IDD and patient factors used as stratification variables. In addition, multiple linear regression will be used to assess the association of count of CVD risk factors with IDD vs. non-IDD and patient factors.

References

1. Jacobs DR, Jr., Woo JG, Sinaiko AR, et al. Childhood Cardiovascular Risk Factors and Adult Cardiovascular Events. *N Engl J Med.* May 19 2022;386(20):1877-1888. doi:10.1056/NEJMoa2109191

6. Hagan, J. F., Shaw, J. S., & Duncan, P. M. (2017). Bright futures: Guidelines for health supervision of infants, children, and adolescents: Pocket guide. American Academy of Pediatrics/Bright Futures, 2017. APA, 7th ed.

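### Appendix 1 models the 0–5 count of cardiovascular risk factors by linear regression without a robust variance, so its standard errors are miscalibrated when unequal-sized groups differ in mean count

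*Combined protocol and SAP*

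**What the plan says.** Appendix 1 defines cardiometabolic risk as something that "can be measured across five domains (blood pressure (BP), lipids, glucose/Hgb A1c, smoking, body mass index (BMI", which makes five domains. Its prevalence measures refer to "the prevalence of any risk factor among the five of interest", so the count of risk factors runs from 0 to 5.

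The count is analysed by multiple linear regression in three places of the Analysis Plan:

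- Aim 2, on patient factors.
- Aim 3: "Multiple linear regression will be used to assess the association of count of CVD risk factors with presence of HRSN (0/1". A second set of these models adds interaction terms, to test formally whether the association differs between subgroups.
- Aim 4: "multiple linear regression will be used to assess the association of count of CVD risk factors with IDD vs. non-IDD and patient factors".

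No robust variance, count or ordinal model, or check of assumptions is named for these models. The binary outcomes are handled by logistic regression or chi-square tests.

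On direction, Appendix 1 hypothesis 4 expects that "those with IDD will have increased CVD risk, compared with those with no IDD diagnosis". Hypothesis 3 expects that "Patients with a higher count of HRSN will be more likely to have any CV risk factors". That wording concerns any risk factor rather than the mean count, so it points to the direction of the count contrast only indirectly.

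**The concern.** Ordinary least squares estimates one residual variance for everyone. With groups of unequal size, the larger group dominates that estimate, while the uncertainty of the group contrast comes mainly from the smaller group. For a sum of uncommon binary factors, a group with a higher mean also has a higher variance. If the smaller group has the higher mean, the model understates the standard error.

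Two things are at stake: the coverage of intervals for the count differences, and the error rate of the Aim 3 interaction tests. A null interaction can hold while HRSN has a main effect, so the variances still differ under the null being tested. More patients do not help, because the ratio of model to true standard error does not depend on sample size.

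**Working it through.** Appendix 1 gives no sample size, standard deviation or power for these models, so there is no figure of the plan's own to reproduce.

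**Inputs from the documents.** Section 8.2: "16% (n=7,258) of patients age 6-17 years had an elevated BP at initial measurement". Section 5: "Fifteen percent of youth receiving care at these sites are obese". I use these as proxies for the blood-pressure and BMI factors in the reference group.

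**Assumed inputs.** Lipids 5%, glucose 3%, smoking 4%; the smaller group is 5–20% of children; all five prevalences there are 1.25, 1.5 or 2 times higher; factors are independent within a child.

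**Formulas.** With share f in the smaller group, N children in all, and group variances v1 (smaller) and v0 (larger):

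- v = sum of p(1−p) over the five factors
- pooled variance s² = f·v1 + (1−f)·v0
- model variance × N = s²·[1/f + 1/(1−f)]
- true variance × N = v1/f + v0/(1−f)
- SE ratio r = √(model/true); coverage = 2Φ(1.96r) − 1

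**Worked case (prevalence ratio 1.5, f = 5%).**

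- Reference mean = 0.16 + 0.15 + 0.05 + 0.03 + 0.04 = 0.43
- v0 = 0.1344 + 0.1275 + 0.0475 + 0.0291 + 0.0384 = 0.377
- v1, from prevalences 0.24, 0.225, 0.075, 0.045 and 0.06, = 0.526
- s² = 0.05 × 0.526 + 0.95 × 0.377 = 0.384
- Model = 0.384 × 21.05 = 8.09; true = 10.51 + 0.40 = 10.91
- r = √(8.09/10.91) = 0.86; coverage = 90.9%

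**Grid.**

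| Prevalence ratio | Share 5%: r, coverage | Share 20%: r, coverage |
|---|---|---|
| 1.25 | 0.92, 92.8% | 0.95, 93.6% |
| 1.5 | 0.86, 90.9% | 0.91, 92.4% |
| 2 | 0.79, 87.6% | 0.85, 90.5% |

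Moving the three assumed prevalences within 3–5% changes coverage by only about 0.1 percentage point.

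**Interaction tests (Aim 3).** Suppose the two subgroups have the same baseline prevalences and the same HRSN share, and there is no true interaction on the additive scale. The interaction contrast then has the same SE ratio r, whatever the subgroup split, and type I error is 2[1 − Φ(1.96r)]. For ratios 1.25, 1.5 and 2 this gives 7.2%, 9.1% and 12.4% at a 5% share, and 6.4%, 7.6% and 9.5% at a 20% share.

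**Limits of the effect.**

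- At f = 50%, r = 1 and coverage is 95%.
- At f = 70% and prevalence ratio 1.5, r = √[0.481 × 4.76 / (0.526/0.7 + 0.377/0.3)] = 1.07, so intervals are too wide.
- With equal prevalences, r = 1 at any share.
- At a 5% share, per-factor prevalences of 0.4 against 0.5 give r = 0.98, and 0.5 against 0.6 give 1.02. The effect is gone near a mean count of 2.5.

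**Simulation check.** I used 10,000 children, 1,000 replicates, correlated factors, age, sex and rural covariates, and a common odds ratio of 1.5 or 2 per factor, with smoking at 3%. Pooled-variance intervals covered 90.1% and 87.8% at a 5% share, and 92.8% and 90.3% at 20%. Robust standard errors gave 94.4% at the 5% share and 95.4% at 20%. With no group difference, the main-effect test rejected in 4–6% of replicates.

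**The case against.** The case for leaving this alone has several parts, and most of it stands.

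- **The count models are not the lead analyses.** A reader might infer that these contrasts are what Appendix 1 was written to estimate. The text does not support that. Hypothesis 3 and Aim 4 concern having any risk factor, tested by chi-square and logistic regression, and the Aim 4 count model is introduced as an addition.
- **Main effects yield no false positives from this source.** When equal means bring equal variances, the pooled test is valid. Where a real difference exists, conclusions would rarely change. Assuming 10,000 children and a 5% share, z is 3.8 (model) against 3.5 (true) at prevalence ratio 1.25, and 7.6 against 6.5 at ratio 1.5. This argument does not cover the Aim 3 interaction tests.
- **The size depends on undocumented inputs.** The documents give no IDD or HRSN share. Appendix 1 also notes that lipids and glucose may be measured only in children with obesity or other risk factors. If the count requires those measurements, its mean is higher. With illustrative prevalences of 30, 50, 25, 15 and 5% (mean 1.25) and an odds ratio of 1.5, coverage is 93.6–94.1% at 5–20% shares.
- **The variance estimator is unstated rather than wrongly stated,** and no confidence intervals are mentioned for these models. That is true, but pooled variance is the default reading of multiple linear regression.

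A reader might also infer that siblings with shared social needs inflate the errors further. The documents give no household size, number of siblings or within-household correlation, so no figure can be supported and I make no claim on it.

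**Conclusion.** The point holds in a conditional form. The default standard errors for the count models are miscalibrated whenever groups differ in both mean count and size. Intervals are too narrow if the group with more risk factors is the smaller one, which for IDD and HRSN is plausible but not documented. Under the stated assumptions, 95% intervals cover about 88–94% and the Aim 3 interaction tests have type I error of about 6–12%.

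It would be wrong to infer that the intervals are always too narrow. The direction depends on group shares that the documents do not give, and on a low mean count that only the 15% and 16% rates support. Nor does the point reach the main-effect tests of no difference, the chi-square and logistic analyses, or the trial's hypotheses H1–H4 in section 8.1. Importance is low.

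**What to change.** Add one sentence to the Appendix 1 Analysis Plan: all linear models of the risk-factor count in Aims 2 to 4, including the interaction models, use heteroscedasticity-robust (sandwich) standard errors. In large samples these are valid whichever way the bias runs, so the change does not depend on the assumptions above.

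It needs one option in the regression procedure and no new data. The cost is slightly wider intervals in the scenario that the hypotheses predict. The estimand stays a difference in mean count. A log-link count model would change it to a ratio, and this problem does not require that.
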